Objectives:	Primary: Co-primary outcomes will include confirmed 7- and 90-day period-prevalence abstinence, and days of marijuana use in the past 90 days. All primary outcomes will be based on participant report during the postpartum timeline follow-back interview; the 7- and 90-day dichotomous abstinence measures will be confirmed using results from urine and hair toxicological analysis, respectively. Evidence of use from either the timeline follow-back interview or toxicological testing will result in that participant being considered non-abstinent.
	Secondary: Secondary outcomes will include (a) birth outcomes from the Electronic Medical Record (EMR), including birth weight, length of hospitalization, and days in Neonatal Intensive Care; (b) help-seeking, particularly engagement in treatment services for marijuana use; (c) comparisons of the three intervention configurations (SBIRT only, texting only, or combined) to each other, rather than to the control condition; and (d) comparison of time-control and screen-only control participants.
Population:	Participants will be pregnant women age 18 to 40, 20 weeks or less gestation, seeking care at the WSU UPG or Thea Bowman prenatal care clinics.
Number of Sites:	Wayne State University
Description of Intervention:	This R34 clinical trial planning grant proposes the development and preliminary validation of two high-reach and mutually compatible technology-based interventions for marijuana use during pregnancy: an interactive computer-delivered brief intervention, and a tailored text messaging intervention.
Study Duration:	21 months
Subject Participation Duration:	20 – 36 weeks (From prenatal appointment before 20 weeks gestation until follow-up postpartum)
Estimated Time to Complete Enrollment:	21 months

Schematic of Study Design:

NIDA Program	[name]
Official:	[contact]; [contact] (fax)
	[contact]
Institutions:	Wayne State University
Other Key	[name]
Personnei:	Wayne State University
	[name].
	Wayne State University

1 INTRODUCTION: BACKGROUND INFORMATION AND SCIENTIFIC RATIONALE

1.1 Backgrou nd Information

The public health impact of marijuana is substantial by any measure, particularly with respect to its use during pregnancy. This is true for at least three reasons. First, marijuana is by far the most commonly used illicit drug in the U.S., and marijuana use disorders alone are as prevalent as disorders related to all other drugs combined, including pain relievers (SAHMSA, 2012). This relative prevalence extends to pregnancy: a total of 4.1% of all pregnant women (7.0% of African-American women) report use of marijuana in the past month, as opposed to 1.3% for all other illicit drugs combined (SAHMSA, 2012); this is also markedly higher than the rate of binge alcohol use in the past month (2.6%) among pregnant women. Second, although non-problem use is common, many marijuana users do experience social and health consequences as a result of their use. For example, in a previous sample of 112 post-partum women who reported any marijuana use prior to pregnancy, 85.7% met World Health Organization/ASSIST screener (Newcombe, Humeniuk, Hallet, & Ali, 2003) criteria for a brief intervention; 71.7% reported daily or almost daily desire to use marijuana, 40.2% reported having a friend or family member express concern about their level of use, and 60.8% admitted to previously trying and failing to control their marijuana use. Frequent marijuana use may also be associated with compromised pulmonary functioning (Tetrault et al., 2007), greater tar deposits than from cigarettes (Mehra, Moore, Crothers, Tetrault, & Fiellin, 2006), increased likelihood/exacerbations of schizophrenia (e.g., Moore et al., 2007), and impairments in executive cognitive functioning (Crean, Crane, & Mason, 2011). Third, marijuana use during pregnancy-although inconsistently associated with poor birth outcomes-has been associated with a range of negative neurobehavioral effects (e.g., Minnes, Lang, & Singer, 2011). In addition, ongoing parental use of marijuana after childbirth has also been associated with negative child outcomes, such as increased risk of behavior problems (Chatterji & Markowitz, 2001) and increased marijuana use disorder symptoms at age 18-20 (Buu et al., 2009). Marijuana use in pregnancy cannot be safely ignored.

Marijuana use in pregnancy is substantially under-studied. Despite being by far the most prevalent illicit drug of abuse among pregnant women (Substance Abuse and Mental Health Services Administration, 2012), and despite its now eclipsing tobacco use in at least one sample of pregnant women (Beatty, Svikis, & Ondersma, 2012), there are currently no randomized trials evaluating interventions for marijuana use in this crucial population. This is unacceptable: although evaluated in fewer studies, research suggests that the long-term consequences of prenatal marijuana exposure may be similar to that of other drugs of abuse, with evidence for subtle but meaningful long-term effects on IQ (Goldschmidt, Richardson, Willford, & Day, 2008), academic achievement (Goldschmidt, Richardson, Willford, Severtson, & Day, 2012), response inhibition (Smith, Fried, Hogan, & Cameron, 2004), delinquency (Day, Leech, & Goldschmidt, 2011), and later substance use (Porath & Fried, 2005). Further, unique among all

substances of abuse, marijuana is vigorously promoted as safe by a visible grassroots community without a counterbalancing public health message (Beatty et al., 2012). There is tremendous need for an evidence-based response in this area.

Proactive technology-based interventions may be an ideal first element in a comprehensive response to substance use in pregnancy. Often deployed in primary care settings, such interventions have been proven efficacious (for example, see systematic reviews and meta-analyses by Portnoy, Scott-Sheldon, Johnson, & Carey, 2008; Riper et al., 2009; Rooke, Thorsteinsson, Karpin, Copeland, & Allsop, 2010). Technology-delivered interventions are also uniquely applicable with non-treatment-seeking populations, who may refuse extended treatment but accept a minimal, opportunistic intervention. Their privacy, ease of use, and ability to work independently of medical staff give them very high potential reach, and thus the potential for a substantial population impact. Their potential is further enhanced by the relative ease of implementation in the community.

Study aims are to develop theory-based eSBIRT and text messaging interventions with expert and participant feedback; to randomize 80 pregnant women to eSBIRT, text messaging, combined, or control conditions (n = 20 each, with the control condition being further split between time control and screen-only); and to conduct postpartum follow-up to measure marijuana use and other secondary outcomes.

1.2 Rationale

Importantly, results from our lab (the Parent Health Lab) of similar approaches with tobacco use during pregnancy (DA021668) and prenatal alcohol use (AA020056) have been encouraging. This lends support to the feasibility of the present application, as well as to the larger goal of this line of research: the establishment of a single software package that can flexibly and effectively address multiple substances. Additionally, behavioral science appears to have reached a point in the technology adoption life cycle in which early efforts have begun to give way to systematic reviews that can drive the field forward in important ways.

This R34 clinical trial planning grant therefore proposes the development and preliminary validation of two high-reach and mutually compatible technology-based interventions for marijuana use during pregnancy. The first, a theory-based, synchronous, and highly interactive computer-delivered brief intervention, will be based on an emerging knowledge base regarding key elements of efficacious technology-delivered interventions. The second intervention, a series of tailored text messages, will build on the rich literature regarding key tailoring elements. These interventions will be developed and refined with input from pregnant women who report active use of marijuana, as well as from health care providers. They will subsequently be tested—alone and in combination—in a pilot randomized trial involving 80 women actively using marijuana during pregnancy. This Stage IA and IB pilot work would set the stage for a

confirmatory Stage II trial. It would also produce the first high-reach brief interventions for marijuana use during pregnancy.

1.3 Potential Risks and Benefits

1.3.1 Potential Risks

The primary potential risk of this type of research involves legal/child protective services repercussions due to drug (marijuana) use during pregnancy. Some additional risk may be present due to potential distress regarding evaluation of multiple sensitive areas.

We believe that the risks to participants in this study are minimal, particularly given the positive nature of the intervention and the plan to seek a Federal Certificate of Confidentiality. We believe that the minor risks that are present are justified given the tremendous potential of this research to produce: (a) a method of identifying a large proportion of women using marijuana during pregnancy; and (b) two replicable, high-reach, and low-cost interventions that are designed for pregnant women. These interventions, then, could potentially be presented to large numbers of pregnant women in a way that is financially and logistically feasible

1.3.2 Potential Benefits

Just over half of participants in this study will receive one or more brief, positive interventions designed to promote reductions in marijuana use during pregnancy. These participants and their infants may benefit from the intervention. The other participants in this study will not receive any form of intervention and are not expected to derive any clear benefit.

2 OBJECTIVES

2.1 Study Objectives/Outcome Measures

2.1.1 Primary

Co-primary outcomes will include confirmed 7- and 90-day period-prevalence abstinence, and days of marijuana use in the past 90 days. All primary outcomes will be based on participant report during the postpartum timeline follow-back interview; the 7and 90-day dichotomous abstinence measures will be confirmed using results from urine and hair toxicological analysis, respectively. Evidence of use from either the timeline follow-back interview or toxicological testing will result in that participant being considered non-abstinent.

2.1.2 Second ary

Secondary outcomes will include (a) birth outcomes from the Electronic Medical Record (EMR), including birth weight, length of hospitalization, and days in Neonatal Intensive Care; (b) help-seeking, particularly engagement in treatment services for marijuana use; (c) comparisons of the three intervention configurations (SBIRT only, texting only, or combined) to each other, rather than to the control condition; and (d) comparison of time-control and screen-only control participants.

3 STUDY DESIGN

The first year of this project will be devoted to development of the eSBIRT and text messaging interventions, with refinement following feedback from participants meeting the same inclusion and exclusion criteria as the proposed pilot trial (e.g., pregnant and reporting active marijuana use). All activities in this phase will be the result of close collaboration between the PI and the rest of the investigative team, particularly [name], [name], and [name] (Consultants from University of Michigan and Virginia Commonwealth University). The investigative team will meet regularly with the PI, both individually and as a group via Skype or web conferencing using "GoToMeeting" software to facilitate screen sharing.

Overview

We will initiate the N = 80 pilot randomized trial following development and modification in response to feedback, after participant ratings have exceeded our a priori criteria for acceptability. The primary goal of this phase will be to pilot test the interventions, alone and in combination, to further evaluate feasibility/acceptability, explore potential mechanisms, and inform effect-size estimation. Even with limited power, 2 X 2 designs are ideal for Stage I trials: they provide richer data to inform Stage II and allow collapsing across factors that prove unrelated to outcome (thus making efficient use of available participants), yet maximize the proportion of participants who receive an intervention (facilitating analysis of feasibility and acceptability). Details are provided below.

Participants

Participants will be 80 pregnant women at less than 20 weeks gestation, recruited from a WSU Ob-Gyn clinic and the Thea Bowman family community health clinic (working with the nurse midwife on staff). Participants will be excluded if they are considering termination of the pregnancy or giving the baby up for adoption, are planning to deliver outside of the DMC Hutzel Hospital (over 90% of patients at this clinic deliver at Hutzel), are deemed unable to understand the consent process, or are unable to understand spoken English. We have had clear success using a similar approach in prior studies. Past samples have been predominantly African-American and low-income (e.g., Ondersma, et al., 2007).

Measures

Given the context of data collection, the overall battery was designed to be thorough yet brief. The brief versions of all measures will be repeated at follow-up, along with more extended assessment in key areas. All measures listed below are well validated, commonly used in NIH-funded trials, have been used successfully in our previous work, and/or are taken from the NIDA Clinical Trials Network (CTN) common assessment battery. Urine samples will be analyzed by Redwood Toxicology, Inc., and hair samples by USDTL Laboratories. All measures will be administered via the CIAS ACASI

functionality, other than the questions about use of technology completed on the paper calendar used for the Timeline Follow-back interview.

The baseline assessment battery below will not be administered at baseline to participants in the screen-only control group; however, all measures will be administered to all groups at follow-up. Finally, note that the follow-up assessment battery includes assessment of the usefulness and impact of the intervention materials, as well as of the timing and reasons behind any attempts to quit or cut down on marijuana use. This information will greatly assist us in evaluating the timing and manner of any intervention-related change, and will assist in planning the subsequent Stage II trial.

Table 2. Study measures at baseline and follow-up	Baseline Follo	w-up
 Demographics Drug-Taking Confidence Questionnaire (marijuana self-efficacv) ASSIST substance use screener (7 items per substance CESD-10 (depression) Motivation Measurement Scales (visual analog) Satisfaction with CIAS software Short Index of Problems-Revised Items to inform tailoring (timing/freq, stage, attitudes) Theory of Planned Behavior & Self-Det. Theory Questions Pregnancy related anxiety scale Urine & hair sample (tested for drugs) Birth outcomes (birth weight, gestation, days in hospital/NICU) Substance Use Calendar (TimeLine Follow Back – TLFB) Mini International Neuropsychiatric Interview (MINI) Cannabis Abuse Screening Test (CAST) and ALAC Substance use in home/peer group/significant relationships Conflict Tactics Scale (CTS-II) Brief Child Abuse Potential Inventory (BCAP) Wavne Indirect Drug Use Screener (WIDUS) HRBS (HIV risk measure) Prescription Drug Use Questions Medical Marijuana Use Questions Kirbv Primary Care PTSD Screen (PC-PTSD) Satisfaction with Text message & study Questions about use of technology 	X X X X X X X X X X	· · · · · · · · · · · · · · · · · · ·

3.1 Subject Inclusion/Exclusion Criteria

Inclusion criteria

Age 18 to 40, pregnant, seeking care at the DMC/UHC or Thea Bowman prenatal clinics, able to communicate in English, own a cellphone and willing to receive text messages, willing to allow access to their pending newborn's birth records, less than 20 weeks pregnant, and reporting marijuana use at least twice weekly in the month before becoming pregnant.

Exclusion criteria

Frank cognitive impairment, considering an elective abortion or adoption, not able to communicate in English, not planning to deliver at a DMC hospital, previous or current research participant in a study conducted by [name], or already a participant with the NICHD Perinatal Research Branch.

3.2 Strategies for Recruitment and Retention

Many techniques and communications are employed to orient each participant from enrollment to completion of participation after follow up appointments. This includes all of the correspondences described in the Correspondence Schedule, some of which are detailed here. About one week after enrollment, a research assistant sends a thank you card by mail or email to the participant. A reminder card is mailed about 14 weeks before the participant's due date reminding them about the follow-up when their baby is born. A phone call is made 8 weeks before their due date to serve as an additional reminder and confirm due date and planned hospital for delivery of the infant. Additionally, holiday, Thanksgiving and birthday cards are mailed or emailed if appropriate given dates between original enrollment and birth of infant. Approval to track participants through their medical records was obtained during consent. We have a DMC nurse who checks census for Hutzel hospital to know when participants deliver. Participants are compensated with a \$50 Target gift card at baseline. For the follow-up visit they are compensated with a \$50 Target gift card and an additional \$25 Target gift card if they provide a hair & urine sample.

3.3 Treatment Assignment Procedures

3.3.1 Randomiz ation Procedures

Randomization is determined by CIAS when first given a computer ID during enrollment and baseline data collection at a rate set by research administrators. All participants who screen eligible for the RCT are randomized to one of four conditions: eSBIRT only, Text message only, eSBIRT and Text message, or Control (split evenly between Screen only or Screen & Assessment). The PI and Project Coordinator monitor the randomization rate to ensure that equal numbers of participants are randomized to each condition: 20 to Control (10 to each Screen and Assessment conditions) and 20 to each Intervention condition (eSBIRT, Text, & Both).

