3.3.2 Masking Procedures (if applicable)

This is a blinded study, meaning that outcomes assessor is blinded to the participant's randomization condition, but the PI and Project Coordinator have access to that condition. Participants are informed in the consent form that they will be randomly placed into one of the four conditions. CIAS automatically randomizes all eligible participants to one

condition. At the end of the assessment and intervention package, CIAS delivers a brief summary of the participant's tailoring conditions in order for the research assistant to assure those participants placed into the text message condition receives a welcome text.

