5.2 Enrollment/Baseline

Participants meeting all eligibility criteria will be offered participation in the pilot clinical trial. Those providing written informed consent will again be given the Tablet PC and headphones. Participants will then be randomized to one of the five conditions by the CIAS software. Total time spent for each participant will be approximately 10-30 minutes, depending on condition, with the exception of those in the screen only condition (who will be done sconer). Randomization will be stratified on race, age, and frequency of marijuana use prior to pregnancy. This study will include five conditions with an *n* of 20 per intervention condition (e-SBIRT only, texting only, or combined) and 10 per control condition (assessment only or screen only). This reduced *n* for the control conditions will simultaneously allow us to (a) focus analyses on feasibility and acceptability, given that 75% of participants will receive one or more interventions; (b) obtain a full control group for primary analyses, at minimal additional cost/effort, by collapsing the two control conditions (if they—as expected—do not differ significantly from each other); and (c) pilot the addition of a screen-only control group in order to identify any practical or procedural challenges prior to a future Stage II trial.

Table 1. Study arms and associated components

Condition	Screening	Assessment battery	Text preferences	eSBIRT	Tailored texting
1. Screen only control	х				
2. Assessment control	х	х			
3. eSBIRT only	х	х		х	
4. Tailored text only	х	х	х		х
5. eSBIRT + Tailored text	x	x	x	х	х

After determining eligibility by the previously mentioned screening procedures and having the participant indicate interest in continuing, the RA reads through the Trial consent form.

OK great. Here's a form describing this second study in detail. Let's go over it together. If you decide you want to participant in this study you will need to sign 2 copies of this form. You will keep one copy and one copy will be kept in a locked file cabinet at WSU in [name] office.

Allow the participant time to read, review, and ask questions. Once all questions are answered participant must sign 2 copies of the form and answer the quiz to determine they understand the study.

Consent Quiz

1.	Is your participation voluntary?	Correct answers _ Yes

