8 STUDY OVERSIGHT

In addition to the PI's responsibility for oversight, this study will use a DSMB to be consistent with a Financial Conflict of Interest (FCOI) management plan from Wayne State University, resulting from the PI's part ownership of the company that markets the software intervention authoring tool that will be used in this study. (Other elements of this management plan include ensuring that the PI's grants are never charged for use of the software, disclosing the potential COI on all publications and presentations, and noting the potential COI in consent documents.) Members of the DSMB assembled for this study include:

- i. [name], University of Cincinnati School of Medicine. [name] has conducted multiple NIH-funded clinical trials, many under the auspices of NIDA's Clinical Trials Network, and one of which was a study seeking to reduce drug use among pregnant women.
- ii. [name], Wayne State University School of Medicine. [name] has led or been part of multiple NIH-funded clinical trials for smoking or gambling, and as a clinician supervises treatment of opioid-dependent pregnant women.
- iii. [name], Harvard University Medical School/VA Boston Healthcare System. [name] is a leader in brief intervention trials for alcohol use in pregnancy.

Charge of the Board DSMB (e.g., advising PI, sending report to IRB, etc.). The DSMB will review all aspects of the study, including recruitment rate, randomization, AEs, protocol violations, unexpected events, etc., and will advise the PI in terms of maintaining participant safety and confidentiality. They will also be asked to verify that study conduct is not influenced by any potential FCOI. They will be asked to approve a report to be sent to the IRB and to NIDA.

Statement of no conflicts of interest. All DSMB members will sign a form verifying that they have no conflicts of interest with respect to the proposed study. None of the DSMB members are involved in any way in carrying out this study.

Frequency of meetings. The DSMB will receive reports and meet at least annually. Additional meetings may be called, as needed, to respond to SAEs or any other study-related challenges.

PI acknowledgement of requirement to report DSMB activity as part of Annual Progress Report to NIDA. All DSMB activity will be reported to NIDA as part of the annual progress report, as required.

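### A monitored, settable randomisation rate cannot guarantee 20/20/20/10/10, and Section 3.3.1 describes no restriction, lock or change log

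*Combined protocol and SAP*

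**What the plan says.** Section 3.3.1 states that CIAS assigns each eligible woman "at a rate set by research administrators". It does not say who the administrators are, or whether the rate may be changed once enrolment has begun. It continues: "The PI and Project Coordinator monitor the randomization rate to ensure that equal numbers of participants are randomized to each condition". The target is 20 in each of three intervention conditions and 20 controls, split 10 and 10.

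Under Section 3.3.2 the outcome assessor is blinded, but "the PI and Project Coordinator have access to that condition". Section 8 records the PI's "part ownership of the company that markets the software intervention authoring tool" and sets up a DSMB for that reason. The DSMB reviews randomisation among other matters, is asked to verify that the conflict does not influence conduct, and meets at least once a year.

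Section 5.2 adds: "Randomization will be stratified on race, age, and frequency of marijuana use prior to pregnancy". Section 3.3.1 does not mention stratification. No section gives the sequence method, a block size or minimisation rule, the levels of the stratifiers, who holds the list, a lock on the rate, a rule for changing it, or a record of changes.

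**The concern.** Section 3.3.1 relies on watching a rate to obtain exact arm sizes. Watching does not produce exact numbers; restricting the sequence does, and so does altering the rate when the counts drift. Only the watching is described.

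If the rate were altered in response to running counts, the probability of each arm would vary over the 21 months of enrolment given in the Protocol Summary. Arm and enrolment date would then be associated, and the Section 9.3 models contain no term for date. The people following the counts are unblinded, and one has a declared financial interest. Even if nobody acts on that knowledge, the plan leaves nothing by which a later reader could confirm it. The trial is a pilot, but Section 9.1 uses its results to decide whether a Stage II trial should follow.

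**Working it through.** **1. The target.** 20 + 20 + 20 + (10 + 10) = 80, which agrees with the stated total. The ratio is 2:2:2:1:1. The ratio sums to 8, and 80 / 8 = 10.

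**2. What a fixed rate delivers by itself.** Take a rate of 1/4 for each of the four conditions and no restriction.
- SD of one arm: √(80 × 0.25 × 0.75) = 3.9. The 95% range is 13 to 28.
- P(20/20/20/20) = 80! / (20!)⁴ × (1/4)⁸⁰ = 0.0014.
- P(controls split 10/10, given 20) = C(20,10) / 2²⁰ = 0.176.
- P(20/20/20/10/10) = 0.0014 × 0.176 = 0.00025, or 0.025%.
- Median gap between the largest and smallest of the four arms: 9 women (400,000 simulated trials).

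This is a benchmark for what a rate alone can do. It does not describe the trial's design, because Section 5.2 says that randomisation is stratified.

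**3. What a rate change would do (illustration; the mid-trial count is assumed).** Suppose that after 40 women one arm has 7 instead of the expected 10. The SD at that point is √(40 × 0.25 × 0.75) = 2.7, so this is an ordinary deviation. Reaching 20 needs 13 of the next 40, so the rate must rise from 0.25 to 13/40 = 0.325. That arm then has 13/20 = 65% of its women from the second half. The other arms together have (60 − 33)/60 = 45%. If abstinence differed between halves by 10 to 30 percentage points (assumed), an analysis without a time term would be shifted by 0.20 × 0.10 = 0.02 to 0.20 × 0.30 = 0.06. If only counts drove the change, chance would set the direction.

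**4. Precision.** The detectable standardised difference (80% power, two-sided 0.05, normal approximation) is 2.80 × √(1/n₁ + 1/n₂). It is 0.886 at 20 v 20 and 0.915 at 15 v 25. Unequal arms cost little.

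**5. What restriction delivers.** Blocks of 8 in the ratio 2:2:2:1:1:
- One list: ten complete blocks give exactly 20/20/20/10/10.
- Two strata: median gap 2, 97.5th percentile 4.
- Eight strata: median gap 4, 97.5th percentile 7.

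The eight strata assume two levels per factor, race split 85/15 (Section 12.4 expects about 85% African-American women), and age and frequency split evenly.

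**6. Whether three stratifiers help.** With the same eight strata and blocks of 8, the SD of the difference in proportions between one intervention arm and control is:

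| Factor | Stratified | Simple randomisation |
|---|---|---|
| Frequency | 0.064 | 0.162 |
| Age | 0.064 | 0.163 |
| Race | about 0.08 | 0.115 |

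Stratifying reduces imbalance on all three factors.

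**The case against.** The rate may simply mean the allocation ratio, with restriction inside CIAS and the monitoring serving only as verification. Section 5.2 says that randomisation is stratified, which normally implies some restriction. This reading is possible, and it is why the point cannot be put as a fault in conduct. But no section states it, and Section 3.3.1 assigns the task of achieving equal numbers to the monitoring.

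A reader might go further and infer that the PI controls or steers allocation. The documents do not support that. CIAS assigns automatically (Sections 3.3.2, 4.2 and 5.2). Research assistants do the recruiting. The administrators who set the rate are not identified as the PI. Changing a probability does not let anyone choose a given woman's arm. The outcome assessor is blinded, and the DSMB looks at both randomisation and the conflict. What remains is exposure. At the minimum frequency the DSMB would meet once or twice in 21 months (21/12 = 1.75), and the plan provides no change log for it to inspect.

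It is also fair that this is a Stage I pilot without a power requirement. That lowers the stakes, but the remedy is cheap and the effect estimates feed a decision.

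**Conclusion.** The concern holds as a weakness in the stated allocation mechanism. A fixed rate does not secure 20/20/20/10/10 (about 0.025% without restriction), and the plan names no method that would. Equalising by changing the rate would tie arm to date; in the illustration, one arm has 65% of its women from the second half against 45% elsewhere. The resulting shift depends on an assumed time trend. The text does not show that rates are changed. Loss of precision is not the issue.

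A reader might also infer that three stratifiers are too many for 80 women. That does not follow. The number of levels and the method are not given, minimisation would cope with three factors, and under plausible blocking all three are better balanced than under simple randomisation. Dropping race and age as stratifiers would return them to about that level of balance. The stratification should stay, but it needs to be specified.

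**What to change.** In Section 3.3.1, replace the monitored rate with permuted-block lists over the five conditions in the ratio 2:2:2:1:1, generated before first enrolment and locked in CIAS. State that no rate is changed afterwards, or that any change is logged, with date and reason, by someone independent of the PI. Send running counts by arm to the DSMB.

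Carry the Section 5.2 stratification into Section 3.3.1, with the levels of each factor, the block size or minimisation rule, and who holds the lists. In Section 9.3, fit race, age and pre-pregnancy frequency in every efficacy model. At present only baseline frequency is certain to enter; race and age enter only if judged not controlled by randomisation.

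If enrolment has already begun or ended, report the mechanism actually used and every rate change.

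The cost is software configuration and wording, a few more model parameters with 80 women, and arm totals that may differ from 20 by a few women when blocks run within strata. With eight strata, the chance that some intervention arm has 17 or fewer, or 23 or more, is about 25% with blocks of 8. It falls to about 5% with blocks of 4 over the four conditions, the control places then being split evenly. By step 4 of the working, such departures matter little.
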